#### 4. LIST OF ABBREVIATIONS AND DEFINITIONS OF TERMS

The following abbreviations and specialist terms are used in this study protocol.

**Table 4: Abbreviations and Specialist Terms**

Abbreviation	Definition
AE	adverse event
ASO	anti-sense oligonucleotide
ECG	electrocardiogram
BMI	body mass index
CAG	cytosine, adenine, and guanine
CAP	CAG-Age-Product
CFR	Code of Federal Regulations
CGI-S	Clinical Global Impression Severity
COVID-19	coronavirus disease 2019
C max	maximum concentration
CS	clinically significant
C-SSRS	Columbia–Suicide Severity Rating Scale
eCRF	electronic case report form
DEC	Dose Evaluation Committee
ET	Early Termination
FAS	Full Analysis Set
FDA	Food and Drug Administration

Abbreviation	Definition
FSH	follicle-stimulating hormone
GCP	Good Clinical Practice
GEE	generalized estimating equation
GMP	Good Manufacturing Practice
HD	Huntington's Disease
HD-CAB	Huntington's Disease Cognitive Assessment Battery
Hi-DEF	Huntington's Disease Everyday Functioning
HIV	human immunodeficiency virus
HTT	Huntingtin gene
ICF	informed consent form
ICH	International Council for Harmonization of Technical Requirements for Pharmaceuticals for Human Use
IEC	independent ethics committee
IP	investigational product
IRB	institutional review board
IRT	interactive response technology
MedDRA	Medical Dictionary for Regulatory Activities
MoCA	Montreal Cognitive Assessment
NCS	not clinically significant
NMDA	N-methyl-D-aspartate
OTS	One Touch Stockings of Cambridge
PAM	positive allosteric modulator
PK	pharmacokinetic
PRO	patient-reported outcome

Abbreviation	Definition
PTAP	Paced Tapping Test
QTcF	QT corrected according to Fridericia's formula
SAE	serious adverse event
SAP	statistical analysis plan
SD	standard deviation
SDMT	Symbol Digit Modalities Test
Study partner	synonymous with care partner
SUSAR	suspected unexpected serious adverse reaction
TEAE	treatment-emergent adverse event
TFC	Total Functional Capacity
THC	tetrahydrocannabinol
UHDRS	Unified Huntington's Disease Rating Scale
UP	unanticipated problem
US	United States
USM	urgent safety measure
VAS	Visual Analogue Scale

## 5. INTRODUCTION

Huntington's disease (HD) is a rare hereditary neurodegenerative disease characterized by specific motor symptoms, including chorea and rigidity, and deterioration of psychiatric and cognitive function. The motor symptoms can manifest at any age, after which disease progression leads to incapacitation and death. Before the appearance of motor symptoms, psychiatric and cognitive dysfunction predominate (Tabrizi 2012). Cognitive impairment is always present in the course of the disease, even in premanifest gene carriers (Cardoso 2017).

The mechanisms of cognitive changes in HD have not been fully described, but changes in glutamatergic neurotransmission appear to be involved. Reduced glutamate in the posterior cingulate cortex has been correlated with cognitive dysfunction in early manifest HD (Unschuld 2012). N-methyl-D-aspartate (NMDA) receptors are a subtype of glutamate receptor with a fundamental and well documented role in regulating synaptic strength, health, and plasticity (Vyklicky 2014, Yao 2017). NMDA receptors have been found to be dysfunctional in the postmortem brains of HD patients (Albin 1990). Together, these data suggest that lowered NMDA receptor tone may contribute to cognitive dysfunction in HD (Paul 2013).

Preclinical data illustrate that HD patients have reduced plasma levels of a specific oxysterol, 24(S)-hydroxycholesterol (Leoni 2013). This molecule acts as an endogenous positive allosteric modulator (PAM) of the NMDA receptor (Paul 2013) and has been correlated with performance on several cognitive tasks in HD (Lewis 2019). SAGE-718 is a novel oxysterol-based PAM of NMDA receptors with the potential to restore NMDA receptor tone to ameliorate cognitive deficits in HD. SAGE-718 only affects receptor function in the presence of endogenous glutamate, thus it does not directly activate the receptor and is not expected to cause NMDA receptor-associated excitotoxicity.

Sage believes that pre-clinical findings, combined with our early-stage clinical data in patients with HD, support the hypothesis that SAGE-718 may work to restore aberrant NMDA receptor activity in patients with early HD and thereby help to ameliorate cognitive deficits seen in these patients.

### 5.1. Overall Risk/Benefit Assessment

Currently, there are no therapies approved to treat the cognitive or psychiatric changes associated with HD.

SAGE-718 has been well characterized in a comprehensive series of in vitro and in vivo nonclinical studies that have defined its key pharmacology, absorption, distribution, metabolism and excretion, drug-drug interaction, and toxicology findings, including compound-related effects and the reversibility of these changes.

In a radiolabeled rat absorption, distribution, metabolism and excretion study, there was no selective distribution or retention of radioactive SAGE-718 to pigmented tissues and no quantifiable concentration of radioactivity was observed in the eye lens in Long Evans rats, implying that potential risk of phototoxicity is low.

Due to an unexplained mortality early in the 14-day oral repeat-dose rat study at 30 mg/kg/day, a human maximum concentration ( $C_{max}$ ) cap for clinical studies was established from the Day 0 mean  $C_{max}$  (443 ng/mL) in female rats at the 15 mg/kg/day dose level. A 10-fold safety factor

was used to derive the 45 ng/mL clinical exposure cap (see Section 5.2). Across rat and dog nonclinical studies a  $C_{max}$  threshold for observation of convulsions occurred at exposures 20 to 40 times greater than clinically relevant exposures.

No deaths, serious adverse events (SAEs) or treatment emergent adverse events (TEAEs) leading to discontinuation were reported in the completed studies with SAGE-718. A maximum tolerated dose has not been identified yet and no characteristic safety signals have been identified to date. No clinically relevant mean changes from baseline were observed in electrocardiograms (ECGs) or electroencephalograms (EEGs). In addition, there were no treatment-emergent adverse events reported in patients with Huntington's disease that were enrolled in the completed SAGE-718 open label study (718-CLP-102).

Based on the completed studies, the benefit-risk profile of SAGE-718 supports further development in an HD patient population.

The effect of SAGE-718 on cognitive function in participants with Huntington's disease will be evaluated in this randomized, placebo-controlled, double-blind study. Additional data on the effects of SAGE-718 in participants with HD will be collected throughout, [REDACTED]  
[REDACTED].

## 5.2. Dose Justification

SAGE-718 has been well tolerated in both healthy participants and a small cohort of participants with HD in previous clinical studies. However, based on nonclinical findings, the United States Food and Drug Administration (FDA) imposed a median maximum concentration ( $C_{max}$ ) cap of 45 ng/mL. To date, clinical studies with SAGE-718 have used doses that resulted in exposures within this cap and no related adverse events (AEs) leading to discontinuation have been reported. For additional information on exposure caps, see the SAGE-718 Investigator's Brochure.

From a previous study of SAGE-718 administered as an oral solution in healthy participants, repeat doses of 1 mg and a single dose of 3 mg demonstrated evidence consistent with NMDA target engagement. From a 14-day study of SAGE-718 administered as an oral solution in participants with HD, repeat doses of 1 mg showed beneficial effects on cognition assessments. Similarly, from a 14-day study of SAGE-718 administered as a solid tablet in participants with Parkinson's Disease, repeat doses of 3 mg when taken with a meal containing approximately 30 g of dietary fat showed beneficial effects on cognition assessments. The PK exposures in the above scenarios were similar, with individual  $C_{max}$  values ranging from 19.7 to 29.7 ng/mL.

In the present study, SAGE-718 will be administered as a lipid based softgel formulation at a daily dose of 1.2 mg. The lipid formulation has improved bioavailability characteristics compared to solution and tablet forms. The dose is selected to provide pharmacokinetic (PK) exposures similar to those achieved in prior studies that have shown evidence consistent with NMDA target engagement and beneficial effects on assessments of cognition. [REDACTED]  
[REDACTED]

## 6. STUDY OBJECTIVES AND ENDPOINTS

Objectives	Endpoints
Primary	

• To evaluate the effect of SAGE-718 on cognitive performance in participants with Huntington's Disease (HD)

Secondary	
Key Secondary Endpoints:
 

1. CFB to Day 84 on the Unified Huntington's Disease Rating Scale (UHDRS) - Independence Scale

2. CFB to Day 84 on the Trail Making Test Part B a

3. CFB to Day 84 on the One Touch Stockings of Cambridge (OTS)

4. CFB to Day 84 on the Paced Tapping Test (PTAP)

5. CFB to Day 84 in Huntington's Disease Everyday Functioning (Hi-DEF) – at home subdomain score

6. CFB to Day 84 in Clinical Global Impression – Severity (CGI-S) – cognitive status subdomain score

• To evaluate the safety and tolerability of SAGE-718 in participants with HD

	
Safety Endpoint:
 

• Proportion of participants experiencing treatment-emergent adverse events (TEAEs)

• To evaluate additional safety and tolerability parameters of SAGE-718 in participants with HD

	

• CFB in vital signs, clinical laboratory analyses, electrocardiograms (ECGs), and suicidal ideation [REDACTED] [REDACTED] • [REDACTED]

---	---

a Applicable only to the subgroup of participants who can complete Trail Making Part B within the allowable time limit at baseline.

## 7. INVESTIGATIONAL PLAN

### 7.1. Overall Study Design

This is a randomized, placebo-controlled, double-blind study to evaluate the cognitive effects, safety, tolerability, [REDACTED] of SAGE-718 in participants with premanifest or early manifest HD. Participants will be adults with genetically confirmed expansion of the Huntington (HTT) gene cytosine, adenine, and guanine (CAG) trinucleotide repeat at screening who meet diagnostic criteria detailed in the inclusion criteria below (including UHDRS scores and CAG-Age-Product [CAP] scores within specific ranges).

An adult study partner is optional but highly recommended for each participant to support completion of study activities and to answer questions about the participant's condition. For prospective participants and study partners (if applicable), the study will begin with the informed consent process.

Screening, safety, and efficacy will be performed according to the schedule presented in [Table 2](#), [REDACTED] will be performed according to the schedule presented in and [Table 3](#).

Screening assessments will be performed to determine eligibility. Participants and study partners (if applicable) will receive training on the study procedures and devices.

Eligible participants will be randomized 1:1 to receive either SAGE-718 (1.2 mg at Day 1 visit through the day prior to Day 28 visit and 0.9 mg from Day 28 visit until End of Treatment [EOT]) or placebo for 84 days. Beginning on Day 1 and continuing through Day 84, participants will self-administer blinded investigational product (IP) once per day in the morning. IP administration will be monitored via a medication adherence monitoring platform used on smartphones to visually confirm IP ingestion. At clinic visits, participants will take the IP under staff supervision, followed by assessments of cognitive function, [REDACTED]

[REDACTED]. Study staff will dispense sufficient IP for daily administration until the next scheduled study visit. Adherence to the dosing regimen will be assessed at each in-clinic visit by review of the medication adherence monitoring platform, examination of the used packaging, and counting any returned tablets.

During the Treatment Period, participants will be able to receive IP as long as there are no dose limiting safety/tolerability concerns. Participants who cannot tolerate 1.2 mg will receive 0.9 mg for the remainder of the Treatment Period. At the discretion of the investigator, participants who cannot tolerate the 0.9 mg dose will be discontinued from IP. Participants who discontinue IP early should complete the remaining study visits as scheduled unless the participant withdraws consent or loses the capacity to grant consent. If a participant withdraws from the study/stops study participation early, an early termination (ET) visit should be conducted. Treatment with SAGE-718 can be ended without down titration.

#### 7.1.1. Screening Period

The Screening Period begins with the informed consent process for prospective participants, including study partners. Subsequent screening assessments will be performed between Day -28 and Day -1 to determine eligibility, including assessments of cognitive function and safety data.

### **7.1.2. Treatment Period**

Eligible participants will be randomized 1:1 to receive either SAGE-718, or placebo for 84 days. Beginning on Day 1 and continuing through the 12-week treatment period, participants will self-administer SAGE-718 or placebo once per day in the morning. Participants who utilize the  $\pm 2$ -day window at Day 84 should continue to self-administer IP within the visit window. IP administration will be monitored using the [REDACTED].

At clinic visits, participants will take the IP under staff supervision, followed by assessments of cognitive function, [REDACTED] as outlined in [Table 2](#) and [Figure 1](#). Study staff will dispense sufficient IP for daily administration until the next scheduled study visit. Adherence to the dosing regimen will be assessed at each in-clinic visit by review of the medication adherence monitoring platform, examination of the used packaging, and counting any returned tablets. [REDACTED]  
[REDACTED]  
[REDACTED]

[figure not shown]
### **7.1.3. Follow-up Period**

Follow-up period starts after Day 84 and continuing through Day 112. After completing the Treatment Period, participants will return to the clinic for follow-up visits on Days 98 and 112 (or ET) to collect continued safety and efficacy data.

### **7.1.4. End of Study**

End of study will be achieved when last study participant completes Follow-Up Visit at Day 112 (or ET) or as defined by local country specific requirements, see [Section 20](#) (Appendix 1).

Figure 1: Study Design

Abbreviations: HD = Huntington's Disease; CAG = cytosine, adenine, and guanine; CAP = CAG-Age-Product; [REDACTED]; FN = Functional Scales; HD-CAB = Huntington's Disease Cognitive Assessment Battery; I/E = Inclusion/Exclusion; MoCA = Montreal Cognitive Assessment; [REDACTED]; TFC = Total Functional Capacity.

## 7.2. Number of Participants

Approximately 178 participants will be randomized in the study to obtain 142 evaluable participants. Additional participants may be randomized and dosed to ensure a sufficient number of evaluable participants or if the early discontinuation rate is higher than expected.

### 7.3. Treatment Assignment

Eligible participants will be randomized 1:1 to receive either SAGE-718, or placebo for 84 days. Additional details on randomization and blinding are provided in Section 9.5.

## 7.4. Dose Adjustment Criteria

Individual dose reductions will be permitted.

During the Treatment Period, participants will be able to receive IP as long as there are no dose limiting safety/tolerability concerns. Participants who cannot tolerate 1.2 mg will receive 0.9 mg for the remainder of the Treatment Period.

If dose adjustment is deemed necessary by the investigator at any time during the Treatment Period, the participant will return to the site to return any remaining IP and for the adjusted dose to be dispensed.

At the discretion of the investigator, participants who cannot tolerate the 0.9-mg dose will be discontinued from IP (refer to Section 8.4 for procedures for early IP discontinuation).

Participants are encouraged to continue to come in for assessments following IP discontinuation.

#### 7.4.1. Stopping criteria

If clinical events suspicious for seizure occur after Screening, study drug should be discontinued immediately with appropriate clinical follow-up, including EEG, repeat serum chemistry, urinalysis, and drug/alcohol tests.

#### **7.4.2. Dose Evaluation Committee**

A Dose Evaluation Committee (DEC) will be convened as needed.

#### **7.4.3. Safety Criteria for Adjustment or Stopping Doses**

##### **Dose Modification in Potential Hy's Law Cases**

Dosing with IP for study participants meeting potential Hy's Law criteria (described in Section 12.2.7) should be interrupted until drug-induced living injury (DILI) is ruled out. Participants should be treated accordingly if hepatic laboratory elevations are due to other causes (eg, viral hepatitis, alcohol ingestion, congestive heart failure). If DILI is not ruled out, IP should be permanently discontinued; if DILI is ruled out and upon liver biochemistry returning to normal or baseline levels, dosing with IP may resume, if clinically appropriate and with agreement from the sponsor.

#### **7.5. Criteria for Study Termination**

Sage Therapeutics may terminate this study or any portion of the study at any time for safety reasons including the occurrence of AEs or other findings, suggesting unacceptable risk to participants, or for administrative reasons. In the event of study termination, Sage Therapeutics will provide written notification to the investigator. Investigational sites must promptly notify their institutional review board (IRB)/independent ethics committee (IEC), where required, and initiate withdrawal procedures for participating participants.

#### **7.6. End of Study Definition**

The end of the study is defined as the date of the last visit of the last participant in the study. A participant is considered to have completed the study if he/she has completed all phases of the study including the last visit. See Section 20 (Appendix 1) for country-specific requirements.

## 8. SELECTION AND WITHDRAWAL OF PARTICIPANTS

### 8.1. Participant Inclusion Criteria

Participants must meet all of the following criteria to qualify for participation in this study:

1. Be capable of providing informed consent, in the opinion of the investigator.
2. Have signed an informed consent form (ICF) prior to any study-specific procedures being performed.
3. Agree to adhere to the study requirements.
4. Be capable of complying with study procedures, in the opinion of the investigator.
5. Be at least 25 years old but no older than 65 years of, at the time informed consent is obtained.
6. Meet all the following criteria for HD at Screening (Days -28 to -2):
  - a. Genetically confirmed disease with CAG expansion  $\geq 36$ .
  - b. At Screening, UHDRS-TFC score  $>6$  and  $<13$ , suggesting no more than a moderate level of functional impairment.
  - c. No features of juvenile HD.
7. CAP score  $>70$ , as calculated using the CAP formula:  $AGE \times (CAG - 30) / 6.49$ .
8. Score of 15 to 25 (inclusive) on the Montreal Cognitive Assessment (MoCA) at Screening.
9. Be willing to invite a study partner, if available, who is reliable, competent, and at least 18 years of age to participate in the study.
10. Be ambulatory (use of assistance devices such as a walker or cane is acceptable, as is occasional use of wheelchair, as judged by the investigator. Individuals requiring a wheelchair on a regular basis are excluded), able to travel to the study center, and, judged by the investigator, is likely to be able to continue to travel to the study center to complete study visits for the duration of the study.
11. Agree, if female, to use at least one method of highly effective contraception (refer to Section 9.2.4 for further details on acceptable forms of contraception) during participation in the study and for 30 days following the last dose of study drug, unless they are postmenopausal (defined as no menses for 12 months without an alternative medical cause and confirmed by follicular stimulation hormone [FSH]  $>40$  mIU/mL), permanently sterile (hysterectomy, bilateral salpingectomy, or bilateral oophorectomy), or does not engage in sexual relations which carry a risk of pregnancy.
12. Agree, if male, to use an acceptable method of effective contraception for the duration of study and for 21 days after receiving the last dose of the IP, unless the participant does not engage in sexual relations which carry a risk of pregnancy. Acceptable methos of effective contraception are listed in Section 9.2.4.
13. Agree, if male, to abstain from sperm donation during the Treatment Period and for 21 days after receiving the last dose of IP.

14. Agree to refrain from drugs of abuse for the duration of the study and from alcohol during the 48 hours preceding each study visit.
15. Completion of HD-CAB Trail Making-B Test in <240 seconds at Screening (Days -28 to -2).

## **8.2. Participant Exclusion Criteria**

Participants who meet any of the following criteria are disqualified from participation in this study:

1. Have participated in a previous clinical study of SAGE-718; have previous exposure to gene therapy; have participated in any HD investigational drug, biologic, or device trial within 180 days, or a non-HD drug, biologic, or device trial within 30 days or 5 half-lives (whichever is longer).

(Note: Participants with confirmation of enrollment in the placebo arm of these trials would not be excluded.)

2. Have a diagnosis of an ongoing neurodegenerative condition other than HD, including but not limited to Alzheimer's Disease, vascular dementia, dementia with Lewy bodies, or Parkinson's Disease.
3. Have been diagnosed with and/or treated for any type of cancer (excluding successfully treated locally excised basal cell carcinoma and melanoma in situ) within the past year prior to screening.
4. Had gastric bypass surgery, has a gastric sleeve or lap band, or has had any related procedures that interfere with gastrointestinal transit.
5. Plans to undergo elective surgery during participation in the study.
6. Receive any of the following prohibited medications within 30 days of screening and during participation in the study:
  - a. Medications with potent effects at the NMDA receptor, including memantine, amantadine, ketamine, cycloserine, or related compounds.
  - b. Medications that inhibit cholesterol absorption (eg, ezetimibe).
  - c. Bile acid sequestrants (eg, colestevam, colestipol, cholestyramine).
  - d. Other medications given at doses or in combinations that are likely to have a deleterious effect on cognitive performance, as determined by the investigator.
  - e. Tetrahydrocannabinol (THC)-containing substances (any route of administration), regardless of whether or not they are prescribed.
7. Have current or recent suicidality, defined as follows:
  - a. Suicidal ideation within the past month, as evidenced by a "Yes" on question 4 (active suicidal ideation with some intent to act, without specific plan) or question 5 (active suicidal ideation with specific plan and intent) on the C-SSRS.
  - b. Suicidal behavior within the past year, as evidenced by a "Yes" on any of the 5 C-SSRS Suicidal Behavior items (actual attempt, interrupted attempt, aborted attempt, preparatory acts, or behavior, or suicidal behavior) on the C-SSRS.
  - c. Presenting a serious risk of suicide in the opinion of the investigator.

8. Take any psychotropic medications, including antidepressants and anxiolytics, unless the dose and frequency have been stable for at least 30 days prior to the first IP administration and are expected to remain stable for the duration of the study.
9. Have an ongoing medical or psychiatric condition that, in the opinion of the investigator, may compromise the participant's safety or compliance with study requirements.
10. Have supine vital signs outside of the following ranges at Screening or Baseline (vital sign measurements may be repeated once for initial values outside these ranges):
  - a. Heart rate <50 or >100 bpm,
  - b. Systolic blood pressure <100 or >160 mmHg,
  - c. Diastolic blood pressure <60 or >100 mmHg.
11. Have an alcohol or drug use disorder within the past 2 years, as assessed by the investigator. A positive urine drug screen is exclusionary unless deemed by the investigator to reflect a prescribed medication.
12. Have a history of significant hand injury that would preclude either writing or rapid bimanual computerized responding.
13. Have a history of seizures or epilepsy, with the exception of a single episode of febrile seizures in childhood.
14. Have a history, presence, and/or current evidence of serologic positive results for human immunodeficiency virus (HIV)-1 or HIV-2, hepatitis B, or hepatitis C.
15. Have a history of brain surgery, a significant head injury causing loss of consciousness greater than 30 minutes, or hospitalization due to a brain injury.
16. Have a history, presence, and/or current evidence of intracranial abnormality (eg, stroke, hemorrhage, space-occupying lesion).
17. Have a positive pregnancy test, be pregnant, is lactating, or intend to breastfeed during the study.
18. Be investigative site personnel, sponsor personnel, or an immediate member of their family (spouse, parent, child, or sibling whether biological or legally adopted).
19. Is known to be allergic to any of SAGE-718 excipients, including soy lecithin.

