**13.8. Sample Size and Power**

The study is designed to detect a difference between the placebo and SAGE-718 group in the change from baseline to Day 84 for the primary endpoint, SDMT score. Using a 2-sided test at an alpha level of 0.05, a sample size of approximately 71 evaluable participants per treatment group would provide 90% power to detect a difference of 4 points between the SAGE-718 and placebo arms in the change from baseline to Day 84 in SDMT values, assuming that the SD of the change from baseline in SDMT is 7.3 points.

Assuming a 20% dropout and a 1:1 randomization ratio, approximately 178 randomized participants (89 per treatment group) will be required to obtain 71 evaluable participants per treatment group. Evaluable participants are defined as those randomized participants who receive IP and have a valid baseline and at least 1 postbaseline SDMT assessment. Additional participants may be randomized to ensure a sufficient number of evaluable participants or if the dropout rate is higher than 20%.

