#### 8.4. Safety Analysis

Safety and tolerability of SAGE-718 is a secondary objective of this study. Proportion of participants experienced treatment-emergent adverse events (TEAEs) is one of the secondary endpoints, and change from baseline in vital signs, clinical laboratory analyses, electrocardiograms (ECGs), [REDACTED]

[REDACTED] (Table 11). All safety analysis will be performed on the Safety Set using actual treatment received.

The safety endpoints evaluated at scheduled visits within treatment period are taken as done in nominal visit, without any windowing. If a value is available for a nominal scheduled visit, that value will be used in summary by visit. If scheduled visit value is not available, a value from the specific visit window will be included in summary. For Post-treatment period visits, the choice of the visit will follow the same rule as described in Table 12 and Table 13.

Anytime on treatment, last value on treatment and last value on study will be included in the summaries whenever indicated in the relevant sections below. Anytime on treatment is defined as measurement on or after first dose, on or before the date of last dose. Last value on treatment is defined as the last post-baseline value between first dose of IP (exclusive) and up to the date of last dose of IP (inclusive). Last value on study is defined as the last post-baseline value on or after the first dose of IP and on or before the last date of the study.

No statistical hypothesis testing will be conducted on the safety analyses.

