#### 8.4.4. Vital Signs

Vital signs will include oral temperature(°C), respiratory rate (breaths per minute), heart rate (beats per minute [bpm]), and blood pressures (mmHg). Heart rate and blood pressure were collected in supine position and standing position at all scheduled time points.

Vital sign results and mean changes from baseline will be summarized by scheduled visit. It will also include the summary of last values on treatment and on study assessments.

Potentially clinically significant values as outlined in the table below will be summarized by treatment and for anytime on treatment, last value on treatment, within 28 Days after the last dose of treatment (follow-up period). By-participant listing of vital signs will also be provided.

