**Table 17. Potentially Clinically Significant Values for Vital Sign Parameters**

Vital Sign	Units	Criteria for PCS Values (Observed values)		Criteria for PCS values (Change from Baseline values)	
		High	Low	Increase	Decrease
Heart rate (supine and standing)	Beats/min	>120	<40	NA	NA
Respiratory Rate	Breaths/min	>20	<8	NA	NA
Systolic blood pressure (supine and standing)	mmHg	>180	<90	$\geq$ 30	$\geq$ 30

Vital Sign	Units	Criteria for PCS Values (Observed values)		Criteria for PCS values (Change from Baseline values)	
		High	Low	Increase	Decrease
Diastolic blood pressure (supine and standing)	mmHg	>110	<50	≥20	≥20
Supine – Standing Systolic Blood Pressure	mmHg	≥20			
Supine – Standing Diastolic Blood Pressure	mmHg	≥10			
Orthostatic hypotension: supine – standing SBP and DBP	mmHg	SBP ≥20 and DBP ≥10			
Possible orthostatic hypotension: supine – standing SBP and DBP	mmHg	SBP ≥20 or DBP ≥10			

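### SAP Table 17 counts orthostatic falls on treatment with no baseline condition, so falls already present before the first dose appear as on-treatment cases and attenuate the contrast between arms

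*Protocol*

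**What the plan says.** **Eligibility.** Protocol 8.2 criterion 10 reads "Have supine vital signs outside of the following ranges at Screening or Baseline" and lists heart rate 50–100 bpm, SBP 100–160 mmHg and DBP 60–100 mmHg as the acceptable ranges. Sections 8.1 and 8.2 set no limit for the fall on standing, for QTcF or for the Table 15 laboratory analytes. Criterion 9 leaves other conditions to the investigator's opinion, without a threshold.

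**Baseline data.** Protocol Table 2 (footnote d) schedules supine readings and readings about 1 and 3 minutes after standing at every vital-signs visit. These include Screening and Day 1 before dosing.

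**Counting rule.** SAP 8.4.4 states: "Potentially clinically significant values as outlined in the table below will be summarized by treatment and for anytime on treatment". It adds the last value on treatment and the 28 days after the last dose. SAP 8.4 gives the period: "Anytime on treatment is defined as measurement on or after first dose, on or before the date of last dose". Table 17 has four supine-minus-standing rows: SBP ≥20, DBP ≥10, both, and either. The last is labelled "Possible orthostatic hypotension: supine – standing SBP and DBP". Their change-from-baseline cells are blank.

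**Baseline-referenced displays.** SAP Table 11 plans a normal-range shift for laboratory data but none for vital signs or ECG. Table 16 has QTcF increases of 30 to 60 and above 60 msec. Table 15 has one baseline-referenced rule, creatinine above three times baseline. Table 17 has change criteria for supine and standing SBP (≥30) and DBP (≥20). Section 8.4 rules out hypothesis tests on safety data.

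**The concern.** The orthostatic rows cannot separate a fall that appeared on treatment from one that was there before it. A participant with a 25 mmHg systolic fall at Screening, on Day 1 before dosing and again on Day 14 enters the table exactly as one whose fall first appeared on Day 14.

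Because safety is judged by reading displayed rates, this matters in three ways. Absolute rates in both arms are too high as a description of what emerged on treatment. The ratio between arms is pulled towards 1. Chance imbalance in pre-existing falls adds noise to the comparison. Adverse events in the same SAP are analysed by treatment emergence (onset, or worsening of a pre-existing condition, after the first dose); the PCS counts have no equivalent rule, although the baseline readings are collected.

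**Working it through.** **1. Denominator.** The documents state no PCS or orthostatic rate, so the only planned figure to reproduce is the sample size. Protocol 13.8 works with a two-sided 5% level and an SD of 7.3 for the SDMT change, and claims that "a sample size of approximately 71 evaluable participants per treatment group would provide 90% power to detect a difference of 4 points".

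- Normal approximation: n = 2 × 7.3² × (1.96 + 1.2816)² / 4² = 70.0 per arm. The exact t calculation gives 90.0% power at 71 and 89.6% at 70, so 71 is right.
- With 20% dropout and equal allocation: 71 / 0.80 = 88.75, so 89 per arm and 178 in total.

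I take 89 per arm as the approximate safety denominator.

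**2. Which rows are exposed.**

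- *Supine heart rate and blood pressure.* The eligible ranges lie inside the PCS limits (heart rate <40 or >120, SBP <90 or >180, DBP <50 or >110). No eligible participant is in PCS territory at the qualifying reading, so these rows are essentially unaffected.
- *Orthostatic rows.* Fully exposed. The standing-pressure change rows do not cover them: with supine pressure unchanged, a fall that grows from 0 to 20 mmHg moves standing SBP by 20, below the limit of 30.
- *QTcF bands.* Partly exposed. A participant at 455 msec before and during treatment enters the lowest band with no increase, but the separate increase criteria show that nothing changed.
- *Laboratory limits.* Partly exposed. The shift table uses normal-range categories, not the Table 15 limits, and only creatinine has its own baseline rule.

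**3. Arithmetic of the attenuation.** Let b be baseline prevalence, r the share of baseline cases seen again on treatment (equal in both arms), and p the new-onset rate.

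- Counted rate = b·r + (1 − b)·p
- Counted risk difference = (1 − b)(p_active − p_placebo)

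Assumed values, not from the documents: p = 8% on SAGE-718 and 3% on placebo (difference 5.0 points, ratio 2.7); b = 5%, 10%, 20%; r = 100% or 70%. At b = 10% and r = 100%: 0.10 + 0.90 × 0.08 = 17.2% and 0.10 + 0.90 × 0.03 = 12.7%.

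| b | Counted, r = 100% | Difference (points) | Ratio | Active-arm cases pre-existing | Ratio, r = 70% |
|---|---|---|---|---|---|
| 5% | 12.6% vs 7.85% | 4.75 | 1.6 | 40% | 1.75 |
| 10% | 17.2% vs 12.7% | 4.5 | 1.35 | 58% | 1.46 |
| 20% | 26.4% vs 22.4% | 4.0 | 1.2 | 76% | 1.24 |

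High recurrence is plausible for vital signs. With an assumed 50% chance at each of the four on-treatment visits (Days 14, 28, 56, 84), 1 − 0.5⁴ = 94% recur at least once. ECG and laboratory tests have two such visits (Days 28 and 84), which gives 1 − 0.5² = 75%.

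**4. Noise.** The 95% half-width of the difference is 1.96 × √[(p₁(1 − p₁) + p₂(1 − p₂)) / n].

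- Counting everyone (n = 89, r = 100%): ±8.9, ±10.5 and ±12.6 points at b = 5%, 10% and 20%.
- Counting only those without the fall at baseline (n = 89 × (1 − b) = 84.5, 80.1, 71.2): ±6.8, ±7.0 and ±7.4 points.

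The restricted count recovers the 5.0-point difference and is more precise despite its smaller denominator. Neither count would settle a 5-point difference in a trial of this size.

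**The case against.** The strongest reply is that the table does what its label says. It reports values at any time on treatment and does not claim emergence. Treatment emergence is handled in the safety endpoint itself, the proportion with TEAEs, and vital-sign, ECG and laboratory changes that the investigator considers clinically significant become adverse events. By-participant listings are planned. Randomisation balances pre-existing falls on average, so a spurious difference can arise only by chance. The risk difference keeps 80–95% of its size in the examples, and no test or decision rule depends on it. All of this stands. It makes the point a modest one, but it does not give the reader of Table 17 a way to tell old falls from new ones.

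A reader might also infer two stronger things that the documents do not support:

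- *That exclusion 10 is at fault because it is supine only.* It is not an error. For supine heart rate and blood pressure it prevents the very problem described here. The gap lies in how the SAP counts.
- *That the SAP ignores baseline for QTcF and laboratory values.* It does not: it has the QTcF increase criteria, the laboratory shift table, the creatinine rule and planned change-from-baseline summaries. What remains is that none of these applies the QTcF bands or most Table 15 limits conditionally on baseline.

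**Conclusion.** The point holds for the four orthostatic rows of SAP Table 17. A fall present before the first dose is counted as an on-treatment PCS case, and no other planned summary corrects for it. It holds to a lesser degree for the observed-value QTcF bands and laboratory limits, and essentially not at all for supine heart rate and blood pressure.

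The direction is certain: with equal recurrence in both arms, the ratio moves towards 1 and the difference is multiplied by (1 − prevalence). If the drug also made existing falls recur more often, the difference would shrink less. The size cannot be fixed from the documents. The figures of about 1.6, 1.35 and 1.2 against a ratio of 2.7 rest on assumed onset rates, assumed prevalence and full recurrence. The expected effect is attenuation rather than a false signal. No inferential result is affected. This is an inexpensive improvement to a descriptive display.

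**What to change.** In SAP 8.4.4, add a treatment-emergent PCS count for the orthostatic rows: criterion met after the first dose and not met at baseline. The denominator is participants who did not meet it at baseline and have a post-baseline value. Show a row with the number meeting the criterion at baseline in each arm, and keep the present unconditional count as supportive.

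Apply the same rule to the QTcF bands in 8.4.3 (a higher band than at baseline) and to the laboratory PCS limits in 8.4.2. The orthostatic rows come first. State also whether the 1-minute or the 3-minute standing reading defines the fall, since 8.4.4 and Table 17 do not say and the baseline flag needs the same rule as the on-treatment one.

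The cost is SAP wording, one derived flag per parameter and a few more table rows. No new data are needed and eligibility is unchanged. The drawback is a smaller denominator where baseline prevalence is high: about 71 per arm instead of 89 at 20%.
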